- d. If ≥ 2 of the first 3 evaluable subjects or ≥ 2 of the 6 evaluable subjects in Dose Level 2 exhibit a DLT in Cycle 1, then **mirdametinib 4 mg BID PO** given continuously will be declared as the recommended dose for Part 2 (RP2D).

6. Dose Level 3 (Dose Level escalation **8 mg BID PO** given continuously)

- a. Up to 3 subjects will be treated with mirdametinib as a single agent at the dose of **8 mg BID PO** in Dose Level 3
- b. If ≤ 1 of the first 3 evaluable subjects in Dose Level 3 exhibit a DLT in Cycle 1, then a sufficient number of subjects will be treated with mirdametinib **8 mg BID PO** given continuously to accrue 6 evaluable subjects.
- c. If ≤ 1 of 6 evaluable subjects in Dose Level 3 exhibit a DLT in Cycle 1, then **mirdametinib 8 mg BID PO** given continuously will be declared as the recommended dose for Part 2 (RP2D).
- d. If ≥ 2 of the first 3 evaluable subjects or ≥ 2 of the 6 evaluable subjects in Dose Level 3 exhibit a DLT in Cycle 1, then **mirdametinib 6 mg BID PO** given continuously will be declared as the recommended dose for Part 2 (RP2D).
- e. The dose of mirdametinib as single agent will not be escalated above **8 mg BID PO** given continuously.

Arm 2 – Part 2 (expansion cohorts for mirdametinib as single agent)

One or more expansion cohorts (up to 30 subjects each) will be started, either in parallel or sequentially depending on the results of Part 1. The purpose will be to evaluate the efficacy and safety of the RP2D of mirdametinib as single agent (as determined in Part 1 of Arm 2) in the subjects with advanced solid cancers (with the exception of colorectal, small bowel, biliary and ampullary cancers) harboring activating mutations in MEK1/2.

Memorial Sloan Kettering Cancer Center
[name]
[name]

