In the dose escalation portion of part 2, we anticipate accruing both class 1 and class 2 MEK alterations. Both of these MEK alteration types are seen commonly and when mature, this dose escalation cohort will comprise patients harboring both mutation types. However, we cannot anticipate the order of accrual on this cohort. If a clear preponderance of one MEK alteration type is accrued first and promising activity is seen, then that expansion cohort will be opened initially, and the other expansion cohort will be opened later, pending clinical activity. If, on the other hand, both class 1 and class 2 MEK alterations accrue at equal rates and promising clinical activity is observed for both alteration types, these will expansion cohorts will open in parallel.

The following expansion treatment groups (up to 30 subjects each) will initially be started, either in parallel or sequentially depending on the efficacy and safety results of Part 1:

1. Class 1 MEK1/2 alterations.
2. Class 2 MEK1/2 alterations.

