For the initial parts of both arms, these utilize 3+3 design with arm 1 utilizing dose de-escalation as necessary, and arm 2 utilizing this design to escalate to MTD or RP2D. In the dose expansion cohorts of arm 1, the mirdametinib RP2D will be administered in combination with the standard recommended dose of fulvestrant with the primarily efficacy endpoint, and in dose expansion cohorts of arm 2, the mirdametinib will be given as monotherapy at the RP2D. Per MSKCC clinical research guidelines in CR426, "Expansion Cohorts in Phase I Clinical Trials", for expansion cohorts of size less than 30, a sample size justification is not required. Further, requirements for stopping rules for lack of efficacy (futility) are also not required for cohorts of less than 30 patients. Assuming a 10% low unpromising response rate (null hypothesis), and a response rate $\geq 25\%$ as a promising rate of response (alternative hypothesis), and $n = 28$ in each expansion cohort, this will provide 86% power to reject the null hypothesis if at the end of the trial at least 5 / 28 responses are observed in each cohort. Type I error is 14% for each

expansion cohort. The 10% null response rate is justified as an approximation of the standard historical rate in breast tumors treated with fulvestrant. For example, the null response rate in Solar-1 trial was 12.8%³³ and the null response rate in the Paloma-3 trial was 6.3%.³⁴

The two arms of the study will be statistically analyzed separately. Given the type I error above of 14% for any one expansion cohort, each arm (with at most two cohorts) yields a family wise error rate of $1-(1-0.14)^2 = 26\%$. If one chooses to consider the (at most) four expansion cohorts simultaneously, this yields an overall family wise error rate of $1-(1-0.14)^4 = 45\%$. While we acknowledge that this is high when all expansion cohorts are considered, first these cohorts are exploratory and second the two arms are clearly biologically different and are being treated with differing drug regimens, therefore they will be analyzed separately, thus the appropriate family wise error rate to consider for this study is that of 2 expansion cohorts, or 26%.

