In the safety run in of arm 1, a minimum of six and as many as 12 DLT-evaluable patients are required. In the dose expansion cohorts of arm 1, the mirdametinib RP2D will be administered in combination with the standard recommended dose of fulvestrant with the primarily efficacy endpoint, and in dose expansion cohorts of arm 2, the mirdametinib will be given as monotherapy at the RP2D. For these expansion cohorts, as explained above, each will be deemed promising if at the end of the study at least 5 / 28 responses (CR or PR) are observed. This part of the study will enroll $2 * 28 = 56$ efficacy evaluable patients (28 patients on each of two expansion cohorts). Exploratory future cohorts, such as subjects with hormone receptor-positive, HER2-negative metastatic breast cancer exhibiting OncoKB defined activating mutations in BRAF, CRAF, or MEK1/2 (section 4.2) are not included in this analysis. To account for non-evaluable patients, we will have a goal total enrollment of 60 patients. This part of the study is planned to accrue approximately 2 patients per month and it is expected to complete accrual in 3 years.

In the dose escalation part of arm 2 (mirdametinib monotherapy in MEK1/2 mutant patients), we anticipate as few as 6 DLT-evaluable patients and as many as 18 DLT-evaluable evaluable patients will be required, the precise number of patients enrolled in this arm is pending the observed toxicity of mirdametinib monotherapy in dose escalation. This part of the study will take approximately nine months to complete accrual, assuming two patients per month are accrued. The specific expansion cohorts for this arm of the trial are pending the observed responses by genotype and cancer lineage in this arm of the protocol. However, as with arm 1, as explained above, each expansion cohort will be deemed promising if at the end of the study at least 5 / 28 responses (CR or PR) are observed. As we also anticipate as many as two expansion cohorts of patients on this arm of the study, this arm will also require as many as $2 * 28 = 56$ efficacy evaluable patients with a goal total enrollment of 60 patients which will take 3 years to accrue.

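### The exemption that 14.5 cites for having no futility rule covers cohorts below 30, but Arm 2 cohorts may enrol 30; one futility look would cost under 1 point of power

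*Combined protocol and SAP*

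**What the plan says.** Section 14.5 (Sample size justification and patient numbers) relies on an institutional guideline on phase I expansion cohorts for two waivers. The first is that "for expansion cohorts of size less than 30, a sample size justification is not required". The second is that "requirements for stopping rules for lack of efficacy (futility) are also not required for cohorts of less than 30 patients". No other reason is given for having no futility rule.

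The same section nevertheless sets a design: a null response rate of 10%, an alternative of 25%, n = 28 per cohort, and success if "at least 5 / 28 responses are observed in each cohort". It states 86% power and 14% type I error per cohort. The rule is applied once, at the end.

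On cohort size the plan gives three figures:

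- **28 evaluable** per cohort, in both arms (14.5).
- **60 enrolled** over two cohorts. For Arm 1: "To account for non-evaluable patients, we will have a goal total enrollment of 60 patients". The same goal is set for Arm 2. The average is 60 / 2 = 30 per cohort.
- **Ceilings in 4.2.** For Arm 2: "One or more expansion cohorts (up to 30 subjects each) will be started", and again "The following expansion treatment groups (up to 30 subjects each) will initially be started". For Arm 1, the ceiling is 28 per cohort.

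**The concern.** Thirty is not less than 30. If the guideline counts enrolled patients, the only reason given for omitting a futility rule does not fit the Arm 2 cohorts as planned.

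Nothing else supplies a numeric efficacy stop for an open cohort. Section 4.2 lets the second Arm 2 cohort open later depending on activity in the first, but gives no threshold and does not close a cohort already open. Section 12.0 frames study termination around risk, toxicity and the risk/benefit balance. Section 16.4 describes committee oversight in general terms, without an efficacy criterion. A cohort with no response in its first 20 patients could therefore fill to its ceiling.

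This matters most in Arm 2. Section 3.6 describes MEK-inhibitor monotherapy in these tumours as an open question, and the 10% null in 14.5 is justified only by fulvestrant results in breast cancer.

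**Working it through.** **Inputs (14.5):** p0 = 0.10, p1 = 0.25, n = 28, success at 5 or more responses. The 5% rate used below is an illustrative assumption for a cohort that does worse than the null.

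**1. The plan's own figures.** P(X ≥ 5), X ~ Bin(28, p):

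- p = 0.10: 0.1421 (stated 14%).
- p = 0.25: 0.8646 (stated 86%).

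Both reproduce.

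**2. Adding one look.** Stop if responses among the first n1 evaluable patients are at most r1; otherwise continue to 28 and keep the rule of 5 or more. The probability of success falls by the chance of stopping a cohort that would have reached 5:

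loss = Σ (x = 0 to r1) P(Bin(n1, p) = x) × P(Bin(28 − n1, p) ≥ 5 − x)

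*Stop at 0 of 14:*

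- p = 0.25: 0.75^14 × P(Bin(14, 0.25) ≥ 5) = 0.0178 × 0.2585 = 0.0046. Power = 0.8646 − 0.0046 = 0.8600.
- p = 0.10: 0.9^14 × P(Bin(14, 0.10) ≥ 5) = 0.2288 × 0.0092 = 0.0021. Type I error = 0.1421 − 0.0021 = 0.1400.

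*Stop at 0 or 1 of 18:*

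- p = 0.25: 0.0056 × 0.0781 + 0.0338 × 0.2241 = 0.0080. Power = 0.8646 − 0.0080 = 0.8566.
- p = 0.10: 0.1501 × 0.0016 + 0.3002 × 0.0128 = 0.0041. Type I error = 0.1421 − 0.0041 = 0.1380.

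| Rule | Type I error | Power | Stops at 5% | Stops at 10% | Stops at 25% |
|---|---|---|---|---|---|
| No look | 14.2% | 86.5% | – | – | – |
| 0 of 14 | 14.0% | 86.0% | 49% | 23% | 1.8% |
| ≤1 of 18 | 13.8% | 85.7% | 77% | 45% | 3.9% |

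The stated 14% and 86% survive at whole-percent rounding, so the family-wise figures of 26% and 45%, which 14.5 computes from 0.14, also stand. Timing matters: stopping at 0 of 10 gives 13.2% and 83.8%, and at ≤1 of 15 gives 12.9% and 83.4%.

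**3. Expected size at a true 10% rate.** If accrual stopped at the look:

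- 0 of 14: 28 − 0.229 × 14 = 24.8.
- ≤1 of 18: 28 − 0.450 × 10 = 23.5.

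Accrual would probably continue. Response must be confirmed at least 4 weeks later (13.4.2, 14.5) and scans are every 8 weeks. The last patient in the look therefore needs about 12 weeks, or 16 weeks on scheduled scans. At about 2 patients per month per arm (14.5), split evenly over two cohorts (an assumption), 3 to 4 more patients enrol:

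- 0 of 14: 28 − 0.229 × 11 = 25.5, to 28 − 0.229 × 10 = 25.7.
- ≤1 of 18: 28 − 0.450 × 7 = 24.9, to 28 − 0.450 × 6 = 25.3.

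If cohorts run one after the other, as 4.2 allows, and all accrual goes to one cohort, 6 to 8 more enrol:

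- 0 of 14: 28 − 0.229 × 8 = 26.2, to 28 − 0.229 × 6 = 26.6.
- ≤1 of 18: 28 − 0.450 × 4 = 26.2, to 28 − 0.450 × 2 = 27.1.

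**The case against.** **The guideline may count evaluable patients.** The paragraph that cites it sets n = 28, and the extra enrolment is there to cover non-evaluable patients. On that count 28 is below 30 and the exemption applies. This stands: the guideline is not in the documents and 14.5 does not say which count is meant. A reader might infer that the exemption plainly fails; the documents do not support so firm a statement.

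**Arm 1 is different.** A reader might infer that cohorts in both arms are set at 30. For Arm 1 that figure is only 60 / 2 from 14.5, and 4.2 sets an explicit ceiling of 28. The Arm 1 issue is a mismatch between two sections.

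**The gain is modest and not free.** A reader might infer that a look leaves the operating characteristics untouched and saves 4 to 5 patients per inactive cohort. Power does fall, an active cohort can be closed wrongly, and the larger saving requires accrual to stop at the look. With accrual continuing the saving is about 2 to 3 patients on average, less if cohorts run in sequence.

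**The cohorts are exploratory and overseen.** Section 14.5 calls them exploratory, a monitoring committee is in place, and there is informal gating of the second Arm 2 cohort. This limits the seriousness of the point, but none of it is a numeric rule for an open cohort.

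**Conclusion.** The point holds in a limited form. On enrolled patients, the exemption in 14.5 does not cover Arm 2 cohorts that may reach 30; on evaluable patients it does, and the plan does not say which count applies. For Arm 1, the 28 in 4.2 and the 30 implied by 14.5 conflict.

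Whichever count applies, one well-timed look keeps the stated 14% and 86% at whole-percent rounding. It lowers power by 0.5 to 0.8 points from 86.5% and wrongly closes a 25%-active cohort 2% to 4% of the time. At a true 10% rate the expected evaluable size is about 25 to 26 rather than 28, assuming about 1 patient per month per cohort, no pause in accrual, and that every patient enrolled during the wait is evaluable. The binomial figures also assume that response status is final at the look; a later first response would be missed.

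No planned analysis is invalidated. The change is worth making before the expansion cohorts open.

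**What to change.** **Preferred.** In 14.5, stop relying on the exemption and add one futility look per cohort, keeping at least 5 of 28 as the final rule. Two workable forms are to close the cohort to accrual if none of the first 14 efficacy-evaluable patients has a confirmed response, or if at most 1 of the first 18 has. The text should state:

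- that the look uses confirmed responses, and when a patient's status is taken as final for it;
- whether accrual continues while the look matures;
- whether Part 1 patients pooled into the efficacy analysis under 14.1 count toward the look and toward the 28.

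**If no look is wanted.** Either keep Arm 2 enrolment below 30 per cohort (at most 2 × 29 = 58 per arm) or state in 14.5 that the guideline counts evaluable patients, after checking that it does.

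**In either case,** reconcile Arm 1 between 4.2 and 14.5.

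**Cost.** These are wording changes. The look costs under 1 point of power, with the wrong-closure risk given above. Limiting enrolment to 29 leaves room for 29 − 28 = 1 non-evaluable patient per cohort instead of 2. Holding Arm 1 to 28 enrolled leaves none, unless pooled Part 1 patients count toward the 28.

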1. Mirdametinib starting dose Dose Level 1 (4 mg BID PO given continuously)
 - a. Up to 3 subjects will be treated with mirdametinib 4 mg BID PO given continuously in combination with the recommended dose of fulvestrant.
 - b. If ≤ 1 of the first 3 evaluable subjects in Dose Level 1 exhibit a DLT in Cycle 1, then Dose Level 1 will be expanded (see #2 below).
 - c. Mirdametinib dose in combination with fulvestrant will not be escalated above the 4 mg BID dose level.
2. Dose Level 1 expansion:
 - a. A sufficient number of subjects will be treated with mirdametinib 4 mg BID PO given continuously in combination with the recommended dose of fulvestrant to accrue 6 evaluable subjects.
 - b. If ≤ 1 of 6 evaluable subjects in the starting Dose Level exhibit a DLT in Cycle 1, then **mirdametinib 4 mg BID PO** given continuously will be declared as the recommended dose for Part 2 (RP2D) in combination with fulvestrant.
 - c. If ≥ 2 of the first 3 evaluable subjects or ≥ 2 of the 6 evaluable subjects in Dose Level 1 exhibit a DLT in Cycle 1, then the mirdametinib dose will be de-escalated (see #3 below, Dose Level -2).

Memorial Sloan Kettering Cancer Center
[name]
[name]

3. Mirdametinib Dose Level -2 (de-escalation Dose Level at 2 mg BID PO given continuously)
 - a. Up to 3 subjects will be treated with mirdametinib 2 mg BID PO given continuously in combination with the recommended dose of fulvestrant in Dose Level -2
 - b. If 1 of the first 3 evaluable subjects in Dose Level -2 exhibit a DLT in Cycle 1, then a sufficient number of subjects will be treated with mirdametinib 2 mg BID PO given continuously in combination with the recommended dose of fulvestrant to accrue 6 evaluable subjects.
 - c. If ≤ 1 of 6 evaluable subjects in Dose Level -2 exhibit a DLT in Cycle 1, then **mirdametinib 2 mg BID PO** given continuously will be declared as the recommended dose for Part 2 (RP2D) in combination with fulvestrant.
 - d. If ≥ 2 of the first 3 evaluable subjects or ≥ 2 of the 6 evaluable subjects in Dose Level -2 exhibit a DLT in Cycle 1, then the Arm 1 will be further de-escalated (see #4 below).
4. Mirdametinib Dose Level -2INT (de-escalation Dose Level at 2 mg BID PO on a 3 weeks on, 1 week off schedule)
 - a. Up to 3 subjects will be treated with mirdametinib 2 mg BID PO given intermittently in combination with the recommended dose of fulvestrant in Dose Level -2INT

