 - b. If 1 of the first 3 evaluable subjects in Dose Level -2INT exhibit a DLT in Cycle 1, then a sufficient number of subjects will be treated with mirdametinib 2 mg BID PO, intermittently dosed, in combination with the recommended dose of fulvestrant to accrue 6 evaluable subjects.
 - c. If ≤ 1 of 6 evaluable subjects in Dose Level -2INT exhibit a DLT in Cycle 1, then **mirdametinib 2 mg BID PO**, intermittently dosed, will be declared as the recommended dose for Part 2 (RP2D) in combination with fulvestrant.
 - d. If ≥ 2 of the first 3 evaluable subjects or ≥ 2 of the 6 evaluable subjects in Dose Level -2 exhibit a DLT in Cycle 1, then the Arm 1 will be discontinued. The reason for discontinuation of Arm 1 will be that 2 mg BID PO, dosed intermittently, is deemed to be the minimum dose required for sufficient clinical benefit from mirdametinib in combination with fulvestrant in the refractory metastatic breast cancer.

Arm 1 - Part 2 (Expansion Cohorts)

The following expansion treatment groups (up to 28 subjects each). Both cohorts are planned and the rationale for sample size is included in section 14.5. These will initially be started, either in parallel or sequentially depending on the results of Part 1:

Memorial Sloan Kettering Cancer Center
[name]
[name]

1. Subjects with hormone receptor-positive, HER2-negative metastatic breast cancer exhibiting NF1 loss defined as homozygous deletion of NF1 by NGS assay; truncating or nonsense mutations in NF1; OncoKB defined pathogenic missense mutation; OncoKB defined activating mutation in KRAS or HRAS.
2. Subjects with hormone receptor-positive, HER2-negative metastatic breast cancer exhibiting EGFR amplification defined as >1.9 copies of EGFR by NGS assay; ERBB2 hotspot somatic mutation defined as activating by OncoKB.

The above expansion treatment groups are prioritized for this study, however as an exploratory treatment group to be considered in the future is the following cohort:

1. Subjects with hormone receptor-positive, HER2-negative metastatic breast cancer exhibiting OncoKB defined activating mutations in BRAF, CRAF, or MEK1/2

Arm 2 – Part 1 (Dose escalation of mirdametinib as single agent)

Part 1 will be conducted in three sequential Dose Level escalations according to the 3+3 design based on the incidence of dose-limiting toxicities (DLT) and the overall safety profile of the study treatments. The DLT definitions are listed in [Section 15.3](#).

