Dose Level -1	3mg PO BID given continuously
Dose Level 1	4mg PO BID given continuously
Dose Level 2	6mg PO BID given continuously
Dose Level 3	8mg PO BID given continuously

In arm 1, dose level 1 of mirdametinib will be used in the safety run-in with fulvestrant and this dose will be used as the RP2D, otherwise dose de-escalation will be carried out. In this arm if that dose is not tolerated, this will proceed to dose level -2 with fulvestrant. If dose level -2 is not tolerated, dose level -2INT will be initiated. Arm 2 will follow a dose escalation 3+3 standard design, in which dose level 1 is the initial dose of mirdametinib, with additional dose levels 2 and 3. Pending DLTs in dose levels 1-3, this arm will proceed to dose level -1 using mirdametinib as monotherapy. If dose level -1 is not tolerated, dose level -1INT will be initiated.

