A sufficient number of subjects will be treated with mirdametinib 4 mg BID PO given continuously in combination with the recommended dose of fulvestrant to accrue at least 6 evaluable subjects. If ≤ 1 of 6 evaluable subjects in the starting dose level exhibit a DLT in Cycle 1, then **mirdametinib 4 mg BID PO** given continuously will be declared as the recommended dose for Part 2 (RP2D) in combination with fulvestrant. If ≥ 2 of the first 3 evaluable subjects or ≥ 2 of the 6 evaluable subjects in Dose Level 1 exhibit a DLT in Cycle 1, then the mirdametinib dose will be de-escalated (Dose Level -2). If dose de-escalation is not required there will be six evaluable patients total.

In the case of de-escalation, Mirdametinib Dose Level -2 (de-escalation dose level 2 mg BID PO) will be given to up to 3 subjects, treated with mirdametinib 2 mg BID PO given continuously in combination with the recommended dose of fulvestrant. If 1 of the first 3 evaluable subjects in Dose Level -2 exhibit a DLT in Cycle 1, then a sufficient number of subjects will be treated with mirdametinib 2 mg BID PO given continuously in combination with the recommended dose of fulvestrant to accrue 6 evaluable subjects. If 1 of 6 evaluable subjects in Dose Level -2 exhibit a DLT in Cycle 1, then **mirdametinib 2 mg BID PO** given continuously will be declared as the recommended dose for Part 2 (RP2D) in combination with fulvestrant. If ≥ 2 of the first 3 evaluable subjects or ≥ 2 of the 6 evaluable subjects in Dose Level -2 exhibit a DLT in Cycle 1, then the Arm 1 will be further de-escalated.

In this case, Mirdametinib Dose Level -2INT (de-escalation dose level at 2 mg BID PO on a 3 weeks on, 1 week off schedule) will be given to up to 3 subjects, treated with mirdametinib 2 mg BID PO on a 3 weeks on 1 week off schedule, in combination with the recommended dose of

Memorial Sloan Kettering Cancer Center
[name]
[name]

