fulvestrant. If 1 of the first 3 evaluable subjects in Dose Level -2INT exhibit a DLT in Cycle 1, then a sufficient number of subjects will be treated with mirdametinib 2 mg BID PO on a 3 weeks on, 1 week off schedule, in combination with the recommended dose of fulvestrant to accrue 6 evaluable subjects. If 1 of 6 evaluable subjects in Dose Level -2INT exhibit a DLT in Cycle 1, then **mirdametinib 2 mg BID PO on a 3 weeks on, 1 week off schedule**, will be declared as the recommended dose for Part 2 (RP2D) in combination with fulvestrant. If ≥ 2 of the first 3 evaluable subjects or ≥ 2 of the 6 evaluable subjects in Dose Level -2INT exhibit a DLT in Cycle 1, then Arm 1 will be discontinued. In the case of de-escalation there will be at least 18 evaluable patients (6 from dose level 0, and 6 on two separate dose levels of de-escalation).

Arm 2

Part 1 will be conducted in three sequential Dose Level escalations according to the 3+3 design based on the incidence of dose-limiting toxicities (DLT) and the overall safety profile of the study treatments. At each step of the 3+3 design, the investigators will review all available safety and PK data in the current Dose Level and decide about the appropriate next step. The subjects will become evaluable for the 3+3 decisions if they complete Cycle 1 and receive at least 80% of assigned drug doses, or if they exhibit a DLT in Cycle 1. The starting dose of mirdametinib as single agent in each dose escalation dose level will be as follows: mirdametinib 4 mg BID PO given continuously, mirdametinib 6 mg BID PO given continuously, mirdametinib 8 mg BID PO given continuously. The de-escalation Dose Levels (Dose Level -1) may evaluate mirdametinib 3 mg BID given continuously and (Dose Level -1INT) may evaluate mirdametinib 3 mg BID given on. 3 weeks on, 1 week off schedule.

The 3+3 decisions in Part 1 of Arm 2 will be made similar to the above. Up to 3 subjects will be treated with mirdametinib as single agent at the dose of **4 mg BID PO** given continuously. If ≤ 1 of the first 3 evaluable subjects in Dose Level 1 exhibit a DLT in Cycle 1, then Dose Level 1 will be expanded. If 0 of the first 3 evaluable subjects in Dose Level 1 exhibit a DLT in Cycle 1, then the dose of mirdametinib as single agent will be escalated to Dose Levels 2 and 3 (**6 mg BID** given continuously **and 8 mg BID** given continuously) following the same rules as above. There will thus be as many as 18 evaluable patients on this arm.

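### The Arm 1 run-in can need up to 18 DLT-evaluable patients, not 12, and some 3+3 rules for zero DLTs are missing, overlapping or ambiguous

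*Combined protocol and SAP*

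**What the plan says.** **Arm 1 count.** Section 14.5 (sample size justification): "In the safety run in of arm 1, a minimum of six and as many as 12 DLT-evaluable patients are required". Section 14.1, on the same run-in: "In the case of de-escalation there will be at least 18 evaluable patients". It builds that figure as 6 patients at the starting level plus 6 at each of two de-escalation levels. Without de-escalation it gives six.

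**Arm 1 levels.** Section 4.2 sets out 4 mg BID (Dose Level 1), 2 mg BID continuous (Dose Level -2) and 2 mg BID three weeks on, one week off (Dose Level -2INT). Section 10.1 gives no patient counts but confirms the third level: "If dose level -2 is not tolerated, dose level -2INT will be initiated".

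**Arm 1 expansion at the lower levels.** Section 4.2 step 3b: "If 1 of the first 3 evaluable subjects in Dose Level -2 exhibit a DLT in Cycle 1, then a sufficient number". Step 4b: "If 1 of the first 3 evaluable subjects in Dose Level -2INT exhibit a DLT in Cycle 1, then a sufficient number". Section 14.1 uses the same trigger at both levels. Two or more DLTs lead to de-escalation or closure.

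**Arm 1 RP2D at the lower levels.** Section 4.2 step 3c: "If ≤ 1 of 6 evaluable subjects in Dose Level -2 exhibit a DLT in Cycle 1, then" 2 mg is declared. Section 14.1 is narrower: "If 1 of 6 evaluable subjects in Dose Level -2 exhibit a DLT in Cycle 1, then" and "If 1 of 6 evaluable subjects in Dose Level -2INT exhibit a DLT in Cycle 1, then".

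**Arm 2.** In section 4.2, 4 mg expands on exactly 1 of 3 and escalates on 0 of 3, while 6 mg and 8 mg expand to six on 0 or 1 of 3. Section 14.1 expands 4 mg on 0 or 1 of 3, also escalates on 0 of 3, and for 6 and 8 mg refers back to the preceding rules.

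**The concern.** These are the patient counts and decision rules for the primary safety objective. The document offers a maximum of 12 in one place and a minimum of 18 in another for the same run-in. The rules themselves give neither bound.

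The result with no written action at the 2 mg levels, no DLT in the first three patients, is the favourable one. It is also the likeliest single result whenever the DLT risk at that level is below 0.25. In Arm 2, someone working from section 14.1 alone would find two instructions for 0 of 3 at 4 mg, and could not tell whether moving from 6 to 8 mg needs three or six evaluable patients.

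**Working it through.** **1. Reproducing the plan's figures.** Under section 4.2 a level ends at 3 evaluable patients if at least 2 have a DLT, and otherwise runs to 6. The treatment of 0 of 3 at the 2 mg levels is left open for now.

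- One de-escalation level: minimum 6, maximum 6 + 6 = 12. This reproduces section 14.5.
- Two de-escalation levels, as written: minimum 6, maximum 6 + 6 + 6 = 18. The 12 does not reproduce.

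**2. Totals after de-escalation.** If 0 of 3 expands to six:

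- 3 + 6, or 3 + 3 + 3 = 9
- 6 + 6, or 3 + 3 + 6 in any order = 12
- two levels at 6 and one at 3 = 15
- 6 + 6 + 6 = 18

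If 0 of 3 were accepted on three patients, 3 + 3 = 6 is also possible. Under either handling, 18 is the largest total and never the smallest.

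**3. Chance of exceeding 12.** The documents give no DLT risks, so these are assumed. Worked case: risk 0.2 at every level, 0 of 3 expanded.

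- P(0 of 3) = 0.8³ = 0.512; P(1 of 3) = 3 × 0.2 × 0.8² = 0.384; P(≥ 2 of 3) = 0.104; P(≥ 1 of 3) = 0.488
- Level fails on 3: 0.104
- Level fails on 6: 0.512 × 0.104 + 0.384 × 0.488 = 0.2406
- Level 3 runs to 6: 1 − 0.104 = 0.896
- P(N > 12) = 0.2406² + 2 × 0.2406 × 0.104 × 0.896 = 0.0579 + 0.0448 = 0.103

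The same calculation for the other cases:

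| Risk at 4 mg / 2 mg / 2 mg INT | 0 of 3 expanded | 0 of 3 accepted on 3 |
|---|---|---|
| 0.1 / 0.1 / 0.1 | 0.012 | 0.007 |
| 0.2 / 0.2 / 0.2 | 0.103 | 0.062 |
| 0.3 / 0.3 / 0.3 | 0.256 | 0.168 |
| 0.2 / 0.1 / 0.1 | 0.036 | 0.019 |
| 0.3 / 0.15 / 0.1 | 0.115 | 0.058 |

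**4. How often the 0-of-3 gap would be met.** Once Dose Level -2 is open, P(0 of 3) = (1 − p)³ = 0.729, 0.614 and 0.512 at p = 0.10, 0.15 and 0.20. At p = 0.25, 0 of 3 and 1 of 3 are equally likely (0.422 each). The level opens only if 4 mg fails, with probability 1 − [(1 − p)⁶ + 6p(1 − p)⁵] = 0.114, 0.345 and 0.580 at p = 0.1, 0.2 and 0.3. The joint probabilities are:

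- 0.1 at both levels: 0.114 × 0.729 = 0.08
- 0.2 at both: 0.345 × 0.512 = 0.18
- 0.2 then 0.1: 0.345 × 0.729 = 0.25
- 0.3 then 0.15: 0.580 × 0.614 = 0.36

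**5. Arm 2, 6 mg to 8 mg.** The section 14.1 table (0.9 / 0.7 / 0.5 / 0.3 / 0.2) is the classical 3+3 to one decimal. The section 4.2 rule always uses six patients unless two of the first three have a DLT.

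| True DLT risk | 0.1 | 0.2 | 0.3 | 0.4 | 0.5 |
|---|---|---|---|---|---|
| Classical: (1 − p)³ + 3p(1 − p)⁵ | 0.91 | 0.71 | 0.49 | 0.31 | 0.17 |
| Section 4.2 at 6 mg: (1 − p)⁶ + 6p(1 − p)⁵ | 0.89 | 0.66 | 0.42 | 0.23 | 0.11 |

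**6. Arm 2 count.** Under section 4.2 the minimum is 3 + 3 = 6 (none of 3 at 4 mg, then at least 2 of 3 at 6 mg) and the maximum 6 + 6 + 6 = 18. The stated 6 to 18 is correct.

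**The case against.** The strongest reply is that context settles most of this. The only route to an RP2D at the 2 mg levels in section 4.2 is a decision on six patients. Section 14.1 counts six at each of them. The parallel Arm 2 steps for 3 mg expand on 0 or 1 of 3. All three point to expansion after 0 of 3. Section 4.2 also has the investigators review the data and choose the next step, so the arm would not stall. The rules that protect patients, for two or more DLTs, are written at every level, apart from one wrong label in step 4d. At Arm 1 Dose Level 1, where every run-in starts, the rules are complete and agree between sections.

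All of that stands. It narrows the rule gap to levels opened after 4 mg fails and makes it a drafting omission. It does not supply the missing rule, and it cannot reconcile 12 with 18.

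A reader might go further on two points that the text does not support.

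- **0 of 6 left without an RP2D in section 14.1.** As written, expansion at the 2 mg levels requires a DLT among the first three, so 0 of 6 cannot arise. The difference in wording begins to matter only once 0 of 3 is also made to expand.
- **Two firm and different rules for 6 to 8 mg.** Section 14.1's back-reference follows one sentence that expands on 0 or 1 of 3 and another that escalates on 0 of 3. It can be read as agreeing with section 4.2. It is ambiguous, and the classical row above describes only one reading of it.

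**Conclusion.** The stated Arm 1 maximum of 12 is wrong. Sections 4.2 and 14.1 give 6 to 18, and section 14.1's minimum of 18 after de-escalation is in fact the maximum. This rests on each level being decided on at most six evaluable patients. Section 14.1 asks for at least six at 4 mg but still takes the decision on six.

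Under equal assumed risks of 0.1, 0.2 and 0.3, the chance of exceeding 12 is about 1%, 6–10% and 17–26%. If risk falls with dose it is 2–4% (0.2/0.1/0.1) or 6–11% (0.3/0.15/0.1). The ranges reflect the two ways of handling 0 of 3.

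The missing action for 0 of 3 at Dose Levels -2 and -2INT, the double instruction for 0 of 3 at Arm 2 Dose Level 1 in section 14.1, and the unclear rule there for Dose Levels 2 and 3 are real but are cured by wording the protocol already uses elsewhere. It would be wrong to infer that the efficacy design is affected: the 28-patient cohorts, their power and type I error do not depend on these figures.

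**What to change.** - **Section 14.5:** give the Arm 1 run-in as 6 to 18 DLT-evaluable patients.
- **Section 14.1, Arm 1:** change the de-escalation total to *up to 18*.
- **Dose Levels -2 and -2INT:** in sections 4.2 and 14.1, expand to six on *≤ 1 of the first 3*. In section 14.1, declare the RP2D on *≤ 1 of 6*, to match section 4.2.
- **Section 14.1, Arm 2:** expand Dose Level 1 on exactly 1 of 3. For Dose Levels 2 and 3, state the section 4.2 rule in full.
- **Escalation table in section 14.1:** add a note that it describes the classical 3+3 and not the six-patient decision from 6 to 8 mg, for which the values are 0.89 / 0.66 / 0.42 / 0.23 / 0.11.
- **Section 4.2 slips:** in Arm 1 step 4d the level should be -2INT; in Arm 2 step 1c the cross-reference should be to #5.

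The cost is wording, plus a stated Arm 1 maximum higher by 18 − 12 = 6. If the accrual of 2 patients per month given for the expansion also held in the run-in, that is 6 / 2 = 3 months, and only if both de-escalation levels open and all three levels fill. The Arm 2 range stays at 6 to 18.
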